## VI. Study Procedures

### a. Subject Selection Procedures

#### i. Sampling plan including Inclusion/Exclusion criteria

We will use convenience and purposive sampling (22) to recruit residents from our testsites in the United States.

We determine our sample size to be 40 in anticipation of 20% dropout rates, which concurs with similar studies. We estimate that a sample size of 32 would allow us to determine the tolerability, acceptability, and feasibility of DW sessions based on similar pilot studies conducted for technological interventions in Alzheimer's disease (18).

#### ii. Recruitment Procedures

##### 1. Where will recruitment occur?

- At the test sites.

##### 2. Where and when will consent be obtained?

- At the sites during a meeting after being interviewed or a week later.

##### 3. Who will obtain consent?

PI and Project Manager

##### 4. What is the advertising plan, if applicable?

- N/A

##### 5. What recruitment materials will be provided to the potential participant (brochures/information sheets/video presentation)?

- Zoom/meeting; Information statement and informed Consent documents

#### iii. Screening Procedures

##### 1. What procedures are required for screening?

- Residents: Discussions with clinical care team and a review of resident's profiles and case notes. We work with care staff to identify resident-participants and their families who have shown a willingness to be involved in previous studies, or who are generally open, enthusiastic and curious to new projects.
- Staff: Discussion with clinical care team to determine suitable care staff. We work with them to identify resident-participants and their families who have shown a willingness to be involved in previous studies, or who are generally open enthusiastic and curious to new projects.

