##### *d. Study outcomes/endpoints*

The study outcome will be a body of evidence that supports our hypothesis: that interactions with ADL content inside the graphical interactive virtual world, DevaWorld, supports completions of actual ADLs.

DevaWorld's feasibility (Aim 1)

Successful primary outcomes are >55% DWS-participation rate and a statistically significant difference between assessments of DWS-participation and non-participation, indicating tolerability and acceptability of routine DWS.

DevaWorld as an assistive tool for preparing and completing ADLs. (Aim2)

Successful secondary outcomes are:

- a reduction in ADL-related care challenges compared to baseline
- reduced time spent on ADLs compared to baseline
- a reduction in negative response behaviors associated with the ADL
- greater interest in the ADL
- a positive shift in care staff attitudes

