## IX. Analysis Plan

*Describe statistical analysis methods as appropriate. For example, will intention-to-treat methodology be used in the analysis? Will there be any sample stratification?*

- Thematic and sentiment analysis of tablet-recorded spoken and visual exchanges during DWS and post-session comments
- Statistical and text analyses of questionnaire responses
  - Statistical Analysis Plan
    - Assessment inventories with scores on the inventory's scale
    - Measuring mean value and standard deviation for the group
    - Complete a superiority statistical test
    - P-values calculated by t-test, 1 sided

HIPAA-compliant data capture software; eg REDCap, will be used to create the database and analyses. <https://www.project-redcap.org/>

Data will be reported graphically or with summary measure (e.g., means and standard errors or median and 95% confidence intervals), and subjected to statistical analysis when appropriate. Completion rates and grades scores will be presented as proportions and percentages.

ADCS-ADL scores will be compared from end of baseline to biweekly scores to the end of intervention and may be analyzed using a paired Student's t-test or the Wilcoxon signed-rank test if the data are not normally distributed.

Completion rates will be the percentage of all dyads who complete the entire eight weeks of study. The ratio of positively graded scores per dyad will be calculated to obtain the level of satisfaction of dyads and indicate the acceptability of DWS.

Aim 1: Successful primary outcomes are >55% completion rate and a statistically significant difference between assessments of completers and non-completers, indicating tolerability and acceptability of routine DWS.

Aim 2: The secondary outcome is to determine the feasibility of DevaWorld as an assistive tool for preparing and completing ADLs. Improved dyad outcomes are less time to complete ADLs, a reduction in negative response behaviors associated with the ADL, greater interest in the ADL, Care staff indicates tasks are easier than before.

Outcomes measures for baseline and intervention will be the same. As the score sheets cover a broader range of ADLs than those depicted in DW, overall and individual ADL scores will be analyzed and subjected to statistical tests. Our null hypothesis will be no statistical differences between ADL scores during the intervention and baseline phases

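### Screening favours residents thought receptive to new projects, so the Aim 1 rate judged against 55% is likely biased upward for eligible long-term care residents

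*Combined protocol and SAP*

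**What the plan says.** Section VI.a.iii (Screening Procedures) describes how candidates are found. The team works with care staff to identify residents and families who were willing to join earlier studies, or who are "generally open, enthusiastic and curious to new projects". The same sentence appears again in the staff bullet. The sampling plan (VI.a.i) states: "We will use convenience and purposive sampling (22) to recruit residents".

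The eligibility list in VI.c.i covers diagnosis or symptoms, recent difficulty with an activity of daily living, language, vision, hearing, pain and ability to sit. It does not mention openness or enthusiasm. It does exclude residents for whom no compatible caregiver is found, and it describes participating staff as motivated.

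The Aim 1 criterion appears in two forms. V.d has "Successful primary outcomes are >55% DWS-participation rate", read together with a second condition as "indicating tolerability and acceptability of routine DWS". IX has "Successful primary outcomes are >55% completion rate", with the denominator given as follows: "Completion rates will be the percentage of all dyads who complete the entire eight weeks of study".

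The design is single-arm (V.a). Section III directs the conclusion at the product's value in long-term care settings, and the end of section II says the evidence will support a case to that sector and to the FDA.

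**The concern.** Aim 1 asks whether residents take to the sessions and tolerate them. If the people approached are those whom staff already regard as receptive, the observed rate describes that subgroup. The plan then sets the rate against a fixed 55% and draws a conclusion about long-term care in general. A pass could partly reflect who was approached. The documents would not let a reader judge how far, because they provide no count of residents who were eligible, approached or declined, and no statement limiting the conclusion to receptive residents.

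**Working it through.** **Step 1: the trait and the endpoint.** Under VI.c.ii, a session goes ahead only if the resident agrees by word or gesture. Listed signs of refusal include ignoring the screen and showing no interest. A resident known for curiosity and openness is plausibly less likely to show those signs, and plausibly more likely to stay for eight weeks. The link is one of correlation. It bears on both forms of the criterion, more directly on participation than on completion.

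**Step 2: is there an offset?** No comparator arm shares the selection, the threshold is fixed, and the only stated denominator is enrolled dyads. Motivated staff and the compatible-caregiver exclusion plausibly push the same way.

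**Step 3: the plan's numbers.** The enrolment figure reproduces from 32 evaluable residents and 20% dropout: 32 / (1 − 0.20) = 40. The 32 itself does not follow from the usual formula at 95% confidence and ±15 points, taking 50% as the rate: 1.96² × 0.5 × 0.5 / 0.15² = 42.7, so 43. That is a separate matter and nothing below depends on it. The plan gives no derivation of 55%.

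**Step 4: a formula for the bias.** Let f be the receptive share of eligible residents, s the receptive share of those enrolled, and p₁ and p₀ the acceptance rates of receptive and other residents.

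- Rate among eligible residents: f·p₁ + (1 − f)·p₀
- Rate among enrolled residents: s·p₁ + (1 − s)·p₀
- Bias: (s − f)(p₁ − p₀)

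The bias is upward whenever s > f and p₁ > p₀. It is zero if the two rates are equal. None of f, s, p₁ or p₀ is in the documents.

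**Step 5: illustration, all rates assumed.** Take s = 1 (only receptive residents enrolled, the extreme case), 40 residents, and one independent yes/no result each. Since 0.55 × 40 = 22, exceeding 55% needs at least 23. Chances of passing are exact binomial tails.

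| f | p₁ / p₀ | Eligible rate | Bias (points) | P(pass), receptive only | P(pass), all eligible |
|---|---|---|---|---|---|
| 0.5 | 55% / 55% | 55% | 0 | 0.439 | 0.439 |
| 0.5 | 60% / 50% | 55% | 5 | 0.689 | 0.439 |
| 0.7 | 65% / 45% | 59% | 6 | 0.876 | 0.641 |
| 0.5 | 65% / 35% | 50% | 15 | 0.876 | 0.215 |
| 0.5 | 70% / 30% | 50% | 20 | 0.968 | 0.215 |
| 0.3 | 65% / 35% | 44% | 21 | 0.876 | 0.060 |

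Partial selection shrinks the bias. With f = 0.5, s = 0.75 and rates of 65% and 35%, it is 0.25 × 30 = 7.5 points.

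With 32 residents, 0.55 × 32 = 17.6, so 18 are needed. The chance of passing is 0.298, 0.517, 0.732 and 0.888 at true rates of 50%, 55%, 60% and 65%.

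The chance of passing is therefore sensitive to shifts of 5 to 15 points when the true rate lies near 55%.

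**The case against.** Purposive sampling is disclosed, this is a small feasibility study, and every consented study enrols willing people. Asking first whether receptive dyads can use the tool is a reasonable early question, and the rate is valid for the people enrolled. All of that stands. It supports a narrower claim, however, and the plan does not make the narrower claim.

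A reader might infer that the plan selects on the outcome itself. The documents do not support this. The trait is general openness, partly the family's, whereas the outcome is how a resident with dementia responds session by session, or whether the dyad lasts eight weeks.

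A reader might also take the screening sentence as a formal entry rule. It describes how candidates are found and does not say that other eligible residents are turned away. Its repetition in the staff bullet may be a drafting carry-over.

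The completion form of the criterion leaves more room. A 20% dropout allowance implies about 80% completion, 25 points above the threshold, so selection need not decide that result. The plan gives no matching expectation for participation.

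Finally, it is tempting to compare participation among everyone approached with 55%. That would count people who declined the study, for example because of the video recording, as having refused the sessions. It mixes consent yield with acceptance and should not be the figure tested.

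**Conclusion.** The concern holds as one of generalisation. Followed as written, the screening approach makes the enrolled-dyad rate likely to overstate acceptance among eligible long-term care residents, and nothing in the documents offsets or measures this. The upward direction rests on two assumptions: that receptive residents are over-represented among those enrolled, and that they accept sessions or complete the study more often. The size is not estimable. The tabulated 0 to 21 points are the product of chosen inputs.

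It would go too far to say that selection turns a failure into a success. Some assumed inputs do that (70% and 30% with f = 0.5 give 50% among all eligible). Others do not (65% and 45% with f = 0.7 give 59%, still above 55%). The study can run as planned; it is the reach of its primary conclusion that is overstated.

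**What to change.** 1. In VI.a.iii, remove the willingness and enthusiasm preference from both bullets, so that residents meeting the VI.c.i criteria are invited without regard to it. No particular order of enrolment is needed.
2. Keep a log of residents eligible, approached, declined (with reason) and enrolled.
3. In IX, report consent yield separately from DWS participation among those enrolled, and compare only the latter with 55%. V.d and IX must first be reconciled on whether 55% applies to participation or completion.
4. If the preference is kept, state in V.d and IX that the 55% result applies only to residents pre-selected as receptive, not to long-term care residents generally. The log is still worth keeping.

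The cost is a wording change and a short log. The downside is possibly slower recruitment and a less favourable rate or, if the preference stays, a narrower claim.

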##### 2. What is the screening schedule (number of visits, length of visits)?

- Clinical team (2 hours)
- One preliminary meeting with care staff (1 hour).

##### 3. Which screening tests/procedures are standard and which are for research purposes only?

- N/A

*b. Consent Process and Timing.*

*i. Process*

Residents

We initiate the consent process by giving residents the opportunity to review the consent form. Proxies, where needed, will receive the consent form as well. (19)

All proxies and residents will be given an opportunity to attend a virtual face-to-face question and answer session, and will be invited to contact the PI directly with further questions.

- Timing for the consent process:

After proxies or residents, as appropriate, have shown comprehension, they will then be permitted to sign the consent form.

Care staff

We initiate the consent process by consulting with the clinical care teams to make a short list of staff who they believe to be well suited to the study.

- Are regular professional care employees
- Are familiar with the care routines

Staff-participant candidates will be invited to attend a virtual or face-to-face question and answer session, and will be invited to contact the PI directly with further questions.

- Timing:

Consent letter to be provided at the Q&A session, after which attendees will be asked to show comprehension. They will then be permitted to sign.

*ii. Who is conducting the consent process and their qualifications?*

PI: [name] and the Project Manager, [name], in collaboration with care team members at the sites.

*iii. If there will be a waiver of consent or of documentation, explain the rationale and regulatory section for the waiver. N/A*

- N/A

*iv. Describe how much time will be given to potential subjects to consider participation.*

- One week to consider
- Opportunity for subject/proxy to attend a Q&A session
- Opportunity for participants to contact the PI with any further questions
- After assurance of comprehension, opportunity to sign consent form in person, or by electronic signature.

*c. Study Assessments and Activities*

*i. Description of participants and what they will be asked to do:*

Residents

Approximately forty residents will be enrolled of any age, gender, or cultural background with a target (though not required) of equal male and female participation. The subject will have a diagnosis of AD/ADRD, or symptoms of an undiagnosed AD/ADRD as observed by professional care staff and confirmed by the head of clinical care. We will neither include

nor exclude participation based on cognitive test scores, however, participants will be given the MMSE test (20) at baseline. Anonymized scores may be referenced in post-study discussions. The participants will have had challenge(s) completing one or more ADLs in the previous month, as discussed at staff meetings, referenced in care plans, or observed/experienced by direct care staff. Ineligible residents are those with significant

non-AD/ADRD neurological, psychiatric, or physical impairment or those who are totally dependent upon others for ADLs.

Other specifications:

- Understand English or Russian.
- Are verbal
- Can sit comfortably for at least 15 minutes in a chair/wheelchair at a table or propped up in bed or princess chair with a tray table
- Are not known to be in pain
- Have good vision, or good corrected vision (i.e., glasses)
- Have good hearing, or good corrected hearing (i.e., aids)
- May sometimes have anxiety or agitation when undertaking ADLs.

Exclusion criteria

- Persons subject to a legal protection order
- Current or planned participation in other research involving neuropsychological evaluations and/or drug trial, up until the end of the current study.
- Informed consent not signed
- Compatible caregiver not found

Staff

Staff are experienced and motivated; are employed at the test site; assist with ADLs will have ADL care experience with residents prior to the study. Their role is to support the participant during a DWS and help them have an optimal session with the app. Staff will receive training on this. After the DWS, staff will assist the resident with their usual ADL routine at times suited to the resident. They will also fillout reports each day.

*ii. List and describe each of the study procedures, assessments, and activities.*

- Initiation session with staff to outline baseline study protocol.
- In the first two weeks of the study to establish baseline, dyads will undertake usual ADL care, i.e., without the DevaWorld Session (DWS) intervention. Staff schedule during baseline:

Mon 40m	Tue 40m	Wed 40m	Thu 40m	Fri 40m
Res A Mouth Care	Res A Mouth Care	Res A Mouth Care	Res A Mouth Care	Res A Mouth Care
Res B Mouth Care	Res B Mouth Care	Res B Mouth Care	Res B Mouth Care	Res B Mouth Care
Res C Mouth Care	Res C Mouth Care	Res C Mouth Care	Res C Mouth Care	Res C Mouth Care
Res Mouth Care	Res Mouth Care	Res Mouth Care	Res Mouth Care	Res Mouth Care
Reporting before end of shift				

- Following baseline and prior to the intervention phase, participating staff will take part in group training, with extra support as needed.
- During the intervention phase, a period of six weeks, the same dyads (or as close to same as is practical) will be assigned a schedule incorporating DWS followed by the same ADL routine as baseline.
- Each resident-participant will have two DWS per week. Staff-participants will spread this load across their shifts, averaging eight DWS sessions per 5-day week. We anticipate that session durations will average five minutes with variability according to resident-participants' individual interest levels on a given day. Staff schedule during study:

Mon 1h 10m	Tue 55m	Wed 1h 10m	Thu 55m	Fri 1h 10m
Res A DWS	Res A Mouth Care	Res A DWS	Res A Mouth Care	Res A Mouth Care
	Res B Mouth Care		Res B DWS	Res B Mouth Care
Res A Mouth Care	Res C DWS	Res A Mouth Care		Res C DWS
Res B DWS		Res B Mouth Care	Res B Mouth Care	
Res C Mouth Care	Res C Mouth Care	Res C Mouth Care	Res C Mouth Care	
Res B Mouth Care	Res D Mouth Care	Res D DWS	Res D Mouth Care	Res D DWS
Res C Mouth Care				
Res D Mouth Care		Res D Mouth Care		Res D Mouth Care
Reporting				

- Procedure for running a DWS

- **Initiating a session:**

Prior to the ADL, the dyad will sit in a quiet nook or the resident's bedroom with appropriate lighting. The care staff will ask the resident if they are comfortable (e.g. need a drink, need to go to the toilet, is comfortably dressed, has glasses and hearing aids in place).

To initiate the session, the care staff will open DevaWorld on the tablet device and invite resident to join.

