**Consent/No consent:**

As the app opens, the care staff will obtain verbal consent (resident uses affirming, positive words or sounds) or non-verbal consent (resident smiles/nods/leans toward the tablet/touches care staff in a positive way/agrees to touch the screen either independently with care staff's support).

If no consent, the caregiver will reapproach in 3-5 minutes, again check if the

person is comfortable, and make any adjustments to improve comfort. Care staff will seek consent again. If consent is not given a second time, the DWS will be dropped and the usual ADL routine will begin.

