**Ongoing Participation or Refusal:**

Staff will record the resident's attitude to the DWS in their daily report. The research team will review these reports daily.

Refusal may be communicated verbally (using negative or anxious words or sounds) or non-verbally (shrugging, shaking head, pushing the tablet away, refusing to put hand to the tablet, not permitting the care staff to hold their hand to support screen tapping, turning their body away, looking away from the app, passive disinterest

If a resident-participant decides that they no longer want to be involved in the study, not just the DWS session for the day, they will be offered DWS sessions daily. After 7 consecutive days of refusals, they will be withdrawn from the study.

(Guidance on the Process Consent method is covered during training and is described below.)

- Plan for 5 mins per session
- Upon consent, care staff initiates the DWS and guides the resident to the part of DevaWorld where the interactive ADL will be explored
- Following the resident's lead in pace and interest, the dyad focuses on helping the DevaWorld characters (male or female) to manage self-care activities in DevaWorld's bathroom and getting him/her ready for bed.
- The session will end when the resident seems ready
- Upon completion of a session, the care staff assists the resident, if needed, to select an emoticon on the end screen before ending the DWS.
- After completing the DWS, the care staff will initiate the planned ADL task, and observe their resident's interactions, cooperation, mood and any behavioral responses.
- Process Consent (21). This method is used during DevaWorld sessions.
  - Staff participant checks consent prior, during and after DW session.  
If Subject indicates their withdrawal of consent, Staff stops and lets the resident withdraw before or during the activity
  - If the resident no longer wants, or is no longer able, to be involved.  
The staff observes residents wishes (verbally or non-verbally) to guide the next steps. Staff then informs the researcher.
  - Depending on the situation, it may or may not be appropriate to ask the resident again later if they would like the opportunity to get involved., The caregiver will reapproach in 3-5 minutes, again check if the person is comfortable, and make any adjustments to improve comfort. Care staff will seek consent again. If consent is not given a second time, the DWS will be dropped and the usual ADL routine will begin.
- Assessments, tools  

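### The comparison with baseline can credit a gain to the whole staff-led DevaWorld session, including its prescribed comfort check and setting, but not to the virtual ADL content alone

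*Combined protocol and SAP*

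**What the plan says.** **Session set-up.** Section VI.c.ii (Procedure for running a DWS, Initiating a session) starts with the setting: "Prior to the ADL, the dyad will sit in a quiet nook or the resident's bedroom with appropriate lighting". The check follows: "The care staff will ask the resident if they are comfortable (e.g. need a drink, need to go to the toilet", with dress, glasses and hearing aids also named. All of this comes before the app is opened. If the resident declines, staff come back after a few minutes and "again check if the person is comfortable, and make any adjustments to improve comfort". After a second refusal, "If consent is not given a second time, the DWS will be dropped and the usual ADL routine will begin".

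**Comparator.** In the first two weeks, "dyads will undertake usual ADL care, i.e., without the DevaWorld Session (DWS) intervention". In the six intervention weeks the dyads "will be assigned a schedule incorporating DWS followed by the same ADL routine as baseline", and "Each resident-participant will have two DWS per week". No section prescribes the quiet place or the comfort check before a baseline ADL, or on an intervention-phase day with no DWS scheduled.

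**What is claimed.** The hypothesis in Section V.d is that "interactions with ADL content inside the graphical interactive virtual world, DevaWorld, supports completions of actual ADLs". The objective in Section III and the hypothesis in the abstract likewise credit the virtual ADLs. Aim 2 in Section III is broader: it concerns the effectiveness of DevaWorld sessions.

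**Design and analysis.** The study has one arm (Section V.a), and the main Aim 2 outcomes are judged against baseline (Section V.d). The null hypothesis in Section IX compares ADL scores between the intervention and baseline phases. No planned analysis separates the set-up from the app content.

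**The concern.** The set-up arrives together with the app. A drink, a toilet visit, or glasses and hearing aids in place could plausibly improve cooperation, mood and ADL time on their own, and so could a few quiet minutes with a staff member. The daily forms time the ADL itself, so a need met before the session falls outside the timed interval, whereas at baseline the same need could fall inside it.

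The stake is attribution. Section II says that the evidence will support the case for DevaWorld as an FDA-credentialed digital therapeutic. For that purpose it matters whether a gain belongs to the software content or to the staff-led session around it. Comparing days with and without a DWS, even on randomised days, would not settle this, because the set-up goes with the session.

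**Working it through.** The plan gives no figure for the effect of the set-up, so there is none to reproduce. The check is a count of exposures, followed by an illustration on assumed values.

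**1. Exposure per resident** (staff schedules in Section VI.c.ii, five mouth-care weekdays)
- Baseline ADLs: 5 × 2 weeks = 10, set-up not prescribed.
- ADLs with a DWS scheduled: 2 × 6 weeks = 12, set-up prescribed.
- Other intervention-phase ADLs: 30 − 12 = 18, set-up not prescribed.
- Share of intervention-phase ADLs with the prescribed set-up: 12/30 = 40%.

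**2. Assumed inputs** (none is in the documents)
- 20% of ADLs (range 10–30%) start with an unmet comfort need.
- Meeting the need saves 3 min of the 10 min scheduled per resident (40 min for four residents).
- Within-resident SD of ADL time is 3 min.
- No informal checks take place on baseline days or days without a DWS, and the content has no effect.

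The number of residents, 32, is from Section V.c.

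**3. DWS days versus baseline**
- Apparent gain: 0.20 × 3 = 0.6 min (0.3–0.9).
- SE = 3 × √(1/12 + 1/10) / √32 = 0.227 min.
- Ratio: 0.6/0.227 = 2.6 SE (1.3–4.0).

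**4. Whole intervention phase versus baseline** (the contrast in the Section IX null hypothesis)
- Apparent gain: 0.40 × 0.6 = 0.24 min (0.12–0.36).
- SE = 3 × √(1/30 + 1/10) / √32 = 0.194 min.
- Ratio: 0.24/0.194 = 1.2 SE (0.6–1.9).

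**5. Two things that shrink these ratios**
- Residents differ in their change. With an assumed SD of change of 1 to 2 min, the DWS-day SE is √(9 × 0.1833 + 1)/√32 = 0.288 to √(9 × 0.1833 + 4)/√32 = 0.420, so 2.6 SE falls to 2.1–1.4. The whole-phase SE is √(9 × 0.1333 + 1)/√32 = 0.262 to √(9 × 0.1333 + 4)/√32 = 0.403, so 1.2 SE falls to 0.9–0.6.
- Staff already check informally. If they do so before half of the ADLs where it is not prescribed, the gain halves: 0.3 min (1.3 SE) for DWS days and 0.12 min (0.6 SE) for the whole phase.

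**6. The same point as a probability.** Take a one-sided paired t-test with n = 32, alpha 0.05 (assumed, since Section IX states none) and no content effect. The chance of a significant gain is 1 − F(t₀.₉₅,₃₁), where F is the noncentral t distribution with 31 df and noncentrality d√32. The whole-phase column multiplies d by 0.4 and keeps the same SD of the difference.

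| Set-up effect d (assumed) | DWS days vs baseline | Whole phase vs baseline |
|---|---|---|
| 0.1 | 0.14 | 0.08 |
| 0.2 | 0.30 | 0.12 |
| 0.3 | 0.51 | 0.16 |
| 0.5 | 0.87 | 0.30 |

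At alpha 0.025 the DWS-day column is 0.08, 0.19, 0.38 and 0.78.

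**The case against.** **The set-up is part of the intervention.** It is a step in running a DWS, and Aim 2 asks about DevaWorld sessions. A reader might infer that the study cannot answer Aim 2. The documents do not support that: a single-arm comparison can address the session as a package, within its usual limits. The mismatch lies only in the sentences that credit the content. This objection stands and sets the scope of the point.

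**Silence is not absence.** A reader might infer that baseline ADLs have no comfort check at all. The documents do not describe what usual care contains, and experienced staff may well ask about a drink or glasses. The contrast is prescribed versus unspecified. This also stands.

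**Set-up and content do not coincide completely.** A twice-refused session leaves an ADL preceded by the set-up without the content. Section VI.c.iv also encourages staff to change their practice on days without the intervention and to note it, so the check may spread. Both are correct, but neither rescues the content claim. Refusal days are self-selected and no analysis of them is planned. Spread of the check blurs the contrast within the phase and leaves the baseline contrast as it was.

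**Why not add the check at baseline?** That would change the usual-care comparator, and one-to-one time and setting would still be tied to the DWS. Content would still not be isolated.

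**This is a feasibility study.** Isolating one component is more than it needs to do, and nothing shows that the check matters more than training or attention. That is fair, and it is why the remedy is limited to recording and wording.

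**Conclusion.** The point holds as a limit on attribution. A gain over baseline could be credited at most to the whole staff-led session (setting, one-to-one time, comfort check and app). The documents give no basis for crediting it to interaction with the virtual ADL content, as Section V.d, the objective in Section III and the abstract do.

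This conclusion follows from the text and needs no numerical assumption. The size of any set-up effect is unknown. The illustration gives about 2.6 SE for DWS days and about 1.2 SE for the whole phase. It rests on an assumed need rate, time saved and SD, on no informal checks, and on no variation between residents in their change. A reader might take 2.6 SE as the expected bias. The documents do not support that: no test of DWS-day ADL time against baseline is specified, and the comparison in Section IX is between phases.

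**What to change.** 1. Add one tick-box to the daily ADL form in both phases: comfort check done, adjustment made. Complete it for every ADL, including those that follow a refused DWS.
2. Report its frequency by phase and by DWS status (delivered, refused, not scheduled). This shows how far usual care already includes the check. It does not isolate a content effect.
3. Reword the hypothesis and conclusion in Section V.d, the objective in Section III and the abstract so that any gain is credited to the whole session and not to the virtual ADL content. Aim 2 can stay as worded.
4. Leave baseline usual care unchanged.

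The cost is one extra form item and a narrower claim, with no added staff, residents or visits. The item may itself prompt some checks at baseline, but it would also record them.
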